2.3.1 Risk/ burden in minors

The expected risk/burden in minors is expected to be similar to subjects over the age of 18 years. The current study proposes similar amounts of investigational product applied/m², regardless of age. The safety profile achieved in minor subjects in the Phase 2A and Phase 2B programs was similar to that of older subjects. Local toxicity and skin reactions will be consistently evaluated throughout the trial in these minor subjects. Risk to children in this program should be compared with lack of on-label alternative products for treatment of congenital ichthyosis in children and adolescents; for example, acitretin is not approved for use in children with congenital ichthyosis in the European Union.

3 OBJECTIVES AND ENDPOINTS

Table 2 Objectives and Endpoints

Objectives	Endpoints
Primary Efficacy Objective	Primary Efficacy Endpoint
To ascertain the efficacy of TMB-001 0.05% topical ointment as a treatment for CI compared with Vehicle during a 12-week treatment.	Comparison of proportions of subjects with ≥ 2 -point changes from Baseline in IGA-scaling and fissuring scores in the Treatment Area at Week 12 between TMB-001 0.05% and vehicle-treated subjects.
Key Secondary Efficacy Objectives	Key Secondary Efficacy Endpoints

 1. To ascertain the efficacy of TMB-001 0.05% topical ointment at Week 12 using the VIIS-50 scaling score. 2. To ascertain the efficacy of TMB-001 0.05% topical ointment at Week 12 using the IGA-scaling and fissuring scores. 3. To evaluate the effect of TMB-001 0.05% topical ointment on subject Itch-QoL scores at Week 12 in subjects with baseline Itch-Numeric Rating Scale (I-NRS) of ≥ 7 	
 1. Comparison of proportion of subjects who achieve 50% reduction from Baseline in VIIS-scaling scores at Week 12 in all areas with Baseline VIIS score ≥ 3 between TMB-001 0.05% and vehicle-treated subjects. 2a. Comparison of proportion of subjects with IGA-scaling and fissuring scores of clear or almost clear at Week 12 between TMB-001 0.05% and vehicle-treated subjects. 2b. Comparison of proportions of subjects who achieve IGA-scaling severity sub-score improvement ≥ 2-points from Baseline to Week 12 between TMB-001 0.05% and vehicle-treated subjects. 3. Comparison of proportion of subjects with ≥ 4-point improvement from baseline in Worst Itch-QoL scores at Week 12 in subjects with baseline Itch-Numeric Rating Scale (I-NRS) of ≥ 7 between TMB-001 0.05% and vehicle-treated subjects.
Other Secondary Efficacy Objectives	Other Secondary Efficacy Endpoints

 4. To ascertain the efficacy of TMB-001 0.05% topical ointment at Week 12 using different levels of VIIS-scaling and IGA-scaling and fissuring scores. 5 To determine optimal maintenance therapy with TMB-001 0.05% topical ointment using the IGA scaling and fissuring scores. 	
 4a. Comparison of proportion of subjects who achieve 25% reduction from Baseline in VIIS-scaling scores at Week 12 in all areas with Baseline VIIS score ≥ 3 between TMB-001 0.05% and vehicle-treated subjects. 4b. Assessment of proportion of subjects with ≥ 2-point improvement from baseline to Week 12 in IGA fissuring severity sub-scores between TMB-001 0.05% and vehicle-treated subjects. 5. Comparison of proportions of subjects with ≥ 2-point changes from Baseline in IGA-scaling and fissuring scores at Week 24 between subjects randomized to TMB-001 0.05% BID and QD maintenance dosing.

6. To determine optimal maintenance therapy with TMB-001 0.05% topical ointment using VIIS-scaling scores.
	
6. Comparison of proportion of subjects who achieve 50% reduction from Baseline in VIIS-scaling scores at Week 24 in all areas with Baseline VIIS score ≥ 3 between subjects randomized to TMB-001 0.05% BID and QD maintenance dosing.


Patient-reported Outcome Measures
 
7. To evaluate the effect of TMB-001 0.05% topical ointment on subject QoL during the 12-week treatment period and subsequent 12-week maintenance period.
	
Patient-reported Outcome Endpoints
 
7a. Comparison of proportions of subjects with ≥ 11-point changes from Baseline in IQOL-32 scores at Week 12 between TMB-001 0.05% and vehicle-treated subjects.
 
7b. Comparison of proportion of subjects with reduction from Baseline in DLQI or CDLQI ≥ 4 points at Week 12 between TMB-001 0.05% and vehicle-treated subjects in adult subjects with Baseline scores ≥ 11 and pediatric subjects with Baseline scores of ≥ 13.
 
7c. Comparison of proportion of subjects with ≥ 4-point changes from Baseline in Itch-QoL scores (in subjects with Baseline I-NRS ≥ 7) at Week 24 between subjects randomized to TMB-001 0.05% BID and QD maintenance dosing.
 
7d. Comparison of proportion of subjects with ≥ 4-point changes from Baseline in DLQI or CDLQI at Week 24 between subjects randomized to TMB-001 0.05% BID and QD maintenance dosing in adult subjects with Baseline scores ≥ 11 and pediatric subjects with Baseline scores of ≥ 13.
 
7e. Comparison of proportion of subjects with ≥ 11-point changes from Baseline in IQOL-32 at Week 24 between subjects randomized to TMB-001 0.05% BID and QD maintenance dosing in adult subjects.

Safety Objectives
 
8. To investigate the safety of topically applied TMB-001 0.05% ointment.
 
9. To evaluate incidence of suspected allergic contact dermatitis
	
Safety Endpoints
 
8a. Comparison of proportion of subjects experiencing LSRs through Week 12 between TMB-001 0.05% and vehicle-treated subjects.
 
8b. Comparison of proportion of subjects experiencing TEAEs through Week 12 between TMB-001 0.05% and vehicle-treated subjects.
 
8c. Comparison of proportion of subjects experiencing LSRs through Week 24 between subjects randomized to TMB-001 0.05% BID and QD maintenance dosing.
 
8d. Comparison of proportion of subjects experiencing TEAEs through Week 24.
 
9. Comparison of proportion of subjects demonstrating clinically confirmed allergic contact dermatitis by patch testing through Week 12 between TMB-001 0.05% and vehicle-treated subjects.

Abbreviations: BID = Twice Daily; CDLQI = Children's Dermatology Life Quality Index; CI = Congenital Ichthyosis; DLQI = Dermatology Life Quality Index; IGA = Investigator's Global Assessment; I-NRS = Itch-Numeric Rating Scale; IQoL = Ichthyosis Quality of Life; QD = Once a Day; LSR = Local Skin Reaction; QoL = Quality of Life; TEAE = Treatment-emergent Adverse Events; VIIS = Visual Index for Ichthyosis Severity.

Table 3 Objectives and Endpoints – Optional Maximal Use Arm

Objectives	Endpoints
Primary Objective	Primary Endpoint
To determine systemic exposure of isotretinoin and metabolites after single or multiple applications of TMB-001 0.05% ointment in subjects with X-linked and autosomal recessive CI.	Assessment of individual concentrations of isotretinoin, tretinoin 4-oxo-tretinoin and 4-oxo-isotretinoin and change from Baseline.
Secondary Objective	Secondary Endpoint
To compare systemic exposure of isotretinoin and metabolites after single or multiple applications of TMB-001 0.05% ointment cross-trial for PK parameters obtained for oral isotretinoin (single dose 80 mg) in healthy volunteers.	Assessment of individual concentrations of metabolites (isotretinoin, tretinoin and 4-oxo-isotretinoin, 4-oxo-tretinoin) and change from Baseline in contemporaneously treated subjects with oral and topical isotretinoin.
Safety Objective	Safety Endpoint
To assess local safety and tolerability of TMB-001 0.05% ointment in adult and pediatric subjects for up to 12 weeks.	Local safety and tolerability based on dermal irritation scale, physical exam and monitoring of AEs.

Abbreviations: AE = Adverse Event; CI = Congenital Ichthyosis; PK = Pharmacokinetic

4 STUDY DESIGN

4.1 Overall Design

[figure not shown]
This is a randomized, double-blind and vehicle-controlled Phase III study to evaluate the safety and efficacy of topical TMB-001 0.05% ointment for the treatment of CI in subjects with either the RXLI or ARCI subtypes.

In addition, a subset of preselected centers will recruit subjects in parallel with either the RXLI or ARCI subtypes for enrollment into an Optional Maximal Use arm for evaluation of the systemic exposure and safety of topical TMB-001 0.05% ointment for the treatment of CI.

Protocol Sections 1 through 8 are applicable for both the Phase III study and the Optional Maximal Use arm, unless otherwise stated. Aspects that are specific to the Optional Maximal Use arm are described in Section 9.

The overall study design is presented in Figure 1.

Figure 1 Overall Study Schema

Abbreviations: ARCI = Autosomal Recessive Congenital Ichthyosis; BID = Twice Daily; IGA = Investigator's Global Assessment; PK = Pharmacokinetic; QD = Once a Day; RXLI = Recessive X-linked Ichthyosis

The Phase III Study is designed in three periods ([Figure 1](#)):

- **Period 1 – Induction (3 weeks):**

At the beginning of the 3-week Induction Period, eligible subjects will be randomized (2:1 ratio) to either TMB-001 0.05% once-a-day (QD) or Vehicle QD treatment, with use of mandatory standardized bland emollient (Cetaphil™) provided by the Sponsor.

- **Period 2 – Treatment (9 weeks):**

The dosing frequency in the 9-week treatment period will be increased in each treatment group to TMB-001 0.05% BID or Vehicle BID. Mandatory bland emollient will be discontinued.

- **Period 3 – Maintenance (12 weeks):**

At Week 12, eligible subjects in the TMB-001 treatment group will be randomized (1:1 ratio) to an open-label treatment with TMB-001 0.05% BID or TMB-001 0.05% QD. To be eligible, subjects must have achieved a ≥ 1 -point reduction in IGA score from Baseline. Subjects with less than a 1-point reduction in IGA score from Baseline will be discontinued from the study.

Vehicle-treated subjects who achieved < 1 -point reduction in IGA score from Baseline are eligible to cross over to the TMB-001 0.05% BID treatment group. Subjects with a ≥ 1 -point reduction in IGA score from Baseline will be discontinued from the study.

Subjects at the end of the study or subjects discontinued from the study at any time will be followed-up for additional 2 weeks for AEs.

Each subject will participate in the study for approximately 36 weeks (including up to a 90-day screening period).

The study will be conducted in approximately 30-40 study centers from United States of America, Canada and several European countries.

4.2 Discussion of Study Design

This is a multicenter, randomized, double-blind, vehicle-controlled Phase III study to evaluate the efficacy and safety of TMB-001 0.05% topical ointment in the treatment of CI. Subjects will be selected according to predefined entry criteria. The study treatment duration is 24 weeks and expected to be sufficient to show a treatment effect.

Isotretinoin is an approved active pharmacological ingredient with a long history of safe use in humans. However, isotretinoin is a known teratogen with an extremely high risk for severe birth defects if pregnancy occur while taking oral isotretinoin in any amount, even for a short period of time. Therefore oral, systemic isotretinoin requires an iPLEDGE program ([iPLEDGE 2012](#)), which is a risk management distribution program mandated by the FDA. To minimize pregnancy risks, WOCBP will only be enrolled if they agree to use highly effective methods of contraception consistently and correctly as described in Table 18 and undergo regular pregnancy testing ([Section 8.3.5](#)).

To minimize bias, subjects will be blinded and randomly assigned to treatment with TMB-001 0.05% or Vehicle ([Figure 1](#)), additionally subjects who had previously been treated with TMB-001 will be excluded from this study but can be enrolled in the optional Maximal Use arm (in a subset of preselected centers). The use of a vehicle control group is consistent with FDA's standard for generating valid scientific evidence to definitively support safety and efficacy. The vehicle group accounts for the effects of treatment that do not depend on the test treatment. The study is designed to mitigate safety risks by using an initial 2:1 randomization (active treatment to vehicle), along with frequent clinic visits over the 12-week treatment period. The subsequent 1:1 randomization of eligible TMB-001 0.05% treated subjects to two dosing regimen (QD or BID) allows for assessment of the optimal TMB-001 0.05% maintenance therapy as well as provides additional safety data for 12 weeks. The cross-over of eligible subjects from the vehicle control group will also provide additional safety data.

Overall, the study design is considered to be scientifically robust and clinically relevant for evaluating TMB-001 0.05% treatment for the safe and effective treatment of CI.

The design of the Optional Maximal Use arm is discussed in [Section 9.1.1](#)

4.3 Justification for Dose

The concentration of TMB-001 0.05% ointment chosen for this study is based on the formulation integrity, the safety and efficacy data from the prior Phase IIa and Phase IIb clinical studies, specific laboratory animal toxicology studies performed by the Sponsor, and a review of the published safety data for isotretinoin. The dose to be applied, TMB-001 0.05%, is based on the potential for therapeutic benefit balanced with the safety risk from the Phase IIb study ([Section 2.1](#)).

4.4 End of Study Definition

A subject is considered to have completed the study if he/she has completed the last scheduled visit (Visit 6 for subjects who do not qualify for maintenance therapy, Visit 9 for subjects who qualify for maintenance therapy) per the SoA ([Table 1](#)). The end of the study is defined as the date of the last visit of the last subject in the study.

The end of study definition of the Optional Maximal Use arm is described in [Section 9.1.2](#).

5 STUDY POPULATION

The following inclusion/exclusion criteria will be used at Visit 1 (Screening) and Visit 2 (Baseline) to determine eligibility for entry into the Phase III study and the Optional Maximal Use arm ([Sections 5.1](#) and [5.2](#)).

5.1 Inclusion Criteria

Subjects must fulfill all of the following inclusion criteria to be eligible for participation:

1. Subject is male or female, 6 years of age and older at Visit 2 (Baseline).
2. Subject has provided written informed consent/assent. A subject under 18 years of age must provide written informed assent and be accompanied by the parent or legal guardian at the time of consent/assent signing. The parent or legal guardian must provide informed consent for the subject. If a subject becomes 18 years of age during the study, the subject must provide written informed consent at that time to continue study participation.
3. Females must be postmenopausal (defined as amenorrhea greater than 12 consecutive months in women 50 years of age and older), surgically sterile (hysterectomy, bilateral salpingectomy, or bilateral oophorectomy), or use 2 acceptable forms of birth control. WOCBP must have a negative serum pregnancy test at screening and negative urine pregnancy test (UPT) at Visit 2 (Baseline) (UPTs must have a minimum sensitivity to detect 25 mIU beta-human chorionic gonadotropin [β -hCG]/mL). Methods of acceptable contraception are further defined in [Appendix 4](#). Female subjects who become sexually active or begin to have relations with a partner during the study must agree to use 2 forms of birth control for 30 days prior to having relations and to continue such forms of birth control for the duration of the study.
4. Subject has clinical diagnosis of CI based upon phenotype and has a genetic confirmation of either ARCI (including but not exclusively transglutaminase 1-deficient, ALOX-12B) or RXLI (e.g., deletion of steroid sulfatase gene) subtypes of CI. Other genetically confirmed ARCI mutations can potentially be enrolled as long as the phenotype is consistent with ARCI and the other inclusion criteria are met, as determined by the Investigator (see [Appendix 5](#)).
5. The amount of CI affected skin in the Treatment Area at Baseline will be between a minimum of 10% and maximum of 90% of the total BSA (1% BSA is approximately equal to the surface area of the subject's palm and fingers, with the fingers extended yet grouped together, creating a flat oval-like surface area).
 - **For the Optional Maximal Use arm:** The amount of CI affected skin in the Treatment Area at Baseline will be between a minimum of 75% and maximum of 90% of the total BSA.
6. Documented history of moderate to severe disease at Screening. Subject's designated VIIS Assessment Areas at Baseline (**not applicable for Optional Maximal Use arm**) MUST:

- Include any of the 4 VIIS Assessment Areas that have some CI disease involving: (a) the upper back from the posterior axillary fold to the other encompassing the T1-T10, (b) the upper arm (excluding elbows), left or right, (c) the shin/lower leg (the portion below the proximal aspect of the kneecap), left or right, and (d) dorsal foot (left or right); AND
- At least 2 of the 4 VIIS Assessment Areas MUST have a scaling score of 3 or more.

7. Subject's IGA score in the Treatment Area at Baseline must be 3 or more.
8. Subject and parent/guardian (if applicable) are willing and able to apply the study treatment(s) as directed, comply with study instructions, and commit to all follow-up visits for the duration of the study.
9. Subject, in the Investigator's opinion, is in good general health and free of any disease state or physical condition that might impair evaluation of the Treatment Areas or exposes the subject to an unacceptable risk by study participation.

5.2 Exclusion Criteria

A subject is ineligible to enter the study if he/she meets 1 or more of the following exclusion criteria:

1. Subject is pregnant, lactating, or is planning to become pregnant during the study.
2. Subject has inflammatory skin diseases that confound the interpretation of results (e.g., atopic dermatitis) unrelated to ichthyosis.
3. Subject has phenotypic clinical presentation and/or genetic abnormality consistent with non-lamellar type or syndromic ichthyoses (including but not exclusively KRT1, KRT10, KRT2, GJB3, GJB4, CDSN)
4. Subject, in the Treatment Areas, has used: (a) any topical prescription or over-the-counter (OTC) therapies (except emollients, keratolytics, and topical steroids – see below), that are intended for, or that in the opinion of the Investigator, may improve CI within 2 weeks of Visit 2 (Baseline), or (b) keratolytics or topical corticosteroids within 5 days prior to Visit 2 (Baseline).
5. Subject, in the Treatment Areas, has used TMB-001 in the past or oral isotretinoin in the past 12 months (**not applicable for Optional Maximal Use arm**).
6. Subject has used any topical products in the Treatment Areas, including bland emollients, on Visit 2 (Baseline).
7. Subject has used ultraviolet (UV) treatment within 4 weeks prior to Visit 2 (Baseline).
8. Subject has undergone systemic therapies using vitamin A supplements or St. John's Wort within 4 weeks prior to Visit 2 (Baseline). *Note: Use of a multivitamin including vitamin A is not exclusionary provided it is taken as directed on the packaging.*

9. Subject is immunosuppressed (e.g., human immunodeficiency virus, systemic malignancy, graft host disease) or receives systemic immunotherapy.
10. Subject is currently taking concomitant immunosuppressive drugs, including systemic corticosteroids, within 2 weeks of Visit 2 (Baseline).
11. Subject has untreated secondary infections; however, subject may become eligible after successful treatment of his/her infection(s) at the Investigator's discretion.
12. Subject is currently enrolled in an investigational drug or device study or has used an investigational drug or investigational device treatment within 30 days or five half-lives prior to Visit 2 (Baseline).
13. Subject has lesions suspicious for skin cancer (if skin cancer is not ruled out by biopsy), a known personal or immediate family history of squamous cell carcinoma of the skin or melanoma or untreated skin cancers within the Treatment Areas.
14. Subject has a physical condition or other dermatologic disorder that, in the Investigator's opinion, might impair evaluation of CI, or that exposes the subject to unacceptable risk by study participation.
15. Subjects with ALT or AST $>2 \times$ Upper Limit of Normal (ULN) and/or creatinine $>1.5 \times$ ULN.
16. Subject is unable to communicate or cooperate with the Investigator due to language problems, impaired cerebral function, or physical limitations.
17. Subject has a history of drug or alcohol abuse within the past 6 months, or if suspected to be noncompliant or is unlikely to comply with the requirements of the study protocol (e.g., due to alcoholism, drug dependency, mental incapacity) in the opinion of the Investigator.
18. Subject has a history of sensitivity to any of the ingredients in the study treatments.

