2.3 Benefit/Risk Assessment

While no topical isotretinoin formulation is approved for use in treatment of CI (or any indication in the US), topical formulations of isotretinoin (e.g., 0.05% gel and 0.1% cream) have demonstrated some efficacy in reducing the clinical signs associated with ichthyosis and other disorders of keratinization. In one study, topical 13-cis-RA (isotretinoin) cream 0.1% demonstrated a marked reduction in scaling and an improvement in skin smoothness after 4 weeks of treatment in 40% of subjects (2/7 subjects with non-erythrodermic LI, 2/2 subjects with Darier's disease, and 0/1 subjects with autosomal dominant ichthyosis vulgaris). However, this clinical improvement was accompanied by local skin irritation (e.g., itchy erythema) in responders, and dose modifications were often prescribed to mitigate such effects ([Steijlen 1993](#)). Similarly, topical isotretinoin gel, 0.05% (Isotrex®) demonstrated partial resolution or clearance of hyperkeratosis and papules in the treatment area (10 cm² area) after 3 months of treatment (up to BID as tolerated) in 50% (6/12) of subjects with Darier's disease. In addition, systemic retinoids, including isotretinoin, have been used for the investigational treatment of CI and have demonstrated remarkable efficacy in reducing the clinical signs of the disease while dosing of the drug is maintained ([Vahlquist 2008](#), [Digiovanna 2013](#)).

The most notable adverse reactions with oral isotretinoin are: teratogenicity, dry lip, dry skin, back pain, dry eye, arthralgia, epistaxis, headache, nasopharyngitis, chapped lips, dermatitis, renal or hepatotoxicity, musculoskeletal discomfort, and visual acuity reduced.

The following are concerns for women of childbearing potential (WOCBP):

- Severe birth defects can occur during pregnancy while taking oral isotretinoin, with any amount and even if taken for short periods of time;
- Pregnancy must be avoided 1 month before, during, and for 1 month after treatment.

As with any retinoid, the side effects of TMB-001 may include the following LSRs: burning, dryness, edema, erythema, hyperpigmentation, hypopigmentation, photosensitivity, pruritus, scaling/peeling, stinging, and tenderness.

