8 STUDY ASSESSMENTS AND PROCEDURES

Study procedures and their timing for both the study and the Optional Maximal Use arm are summarized in the SoA ([Table 1](#) and [Table 13](#)). Adherence to the study design requirements, including those specified in the SoA, is essential and required for study conduct.

All screening evaluations must be completed and reviewed to confirm that potential subjects meet all eligibility criteria. The Investigator will maintain a screening log to record the details of all subjects screened and to confirm eligibility or record reasons for screening failure, as applicable.

Protocol waivers will not be considered for this study and assessments/procedures not completed as per protocol will be recorded as deviations. Acute safety concerns should be discussed with the Sponsor immediately upon occurrence or awareness to determine if the subject should continue or discontinue study treatment.

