8.3.4 Clinical Safety Laboratory Assessments

Urine and blood samples will be collected from each subject for safety laboratory analyses at the time points designated in the SoA ([Table 1](#) and Table 13).

Subjects must be fasting (at least 8 hours) for Visit 1 (Screening) and, if possible, for Visit 6 and the EOS visit; however, if a subject arrives at the clinic for the EOS visit without fasting for at least 8 hours, laboratory specimens may be collected as non-fasting, at the discretion of the Investigator, and with the appropriate fasting status documented on the laboratory requisition form.

See [Appendix 2](#) for the list of clinical laboratory tests to be performed.

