- b. Screening assessments (except for genetic testing) may be performed up to 90 days prior to Visit 2 (Baseline) for those qualified subjects who are eligible to enroll in the study but require washout of medications prior to enrolling into the Treatment Phase of the study. Genetic confirmation should be obtained prior to conducting additional eligibility assessments in the screening period. There is no window for obtaining genetic confirmation, it can be obtained at any time following consent and with no restriction until Visit 2 (Baseline).
- c. Visits 3, 5 and 6 will be performed only in subjects ≥12 years.
- d. Subjects at the end of the study or subjects discontinued from the study at any time will be followed-up for additional 2 weeks for AEs.
- e. For subjects who require genetic testing, or a washout period related to exclusionary medications, reaffirm these subjects meet all protocol requirements at Visit 2 (Baseline).
- f. Examination will include head and neck, dermatologic, cardiovascular, respiratory, gastrointestinal (abdomen), and gross motor and gait assessments. Additional examinations will be conducted at Visit 2 (Baseline) to identify any changes since the Screening, at Visit 8 (EOS) to assess changes throughout the study. Abnormalities at Visit 1 (Screening) and Visit 2 (Baseline) will be recorded as medical history. Any new or worsening abnormality at all subsequent visits will be recorded as AEs.
- g. If there are less than two weeks between Visit 1 (Screening) and Visit 2 (Baseline), the physical examination at the Visit 2 (Baseline) includes only a dermatological assessment.
- h. Clinical laboratory tests (hematology, clinical chemistry, routine urinalysis) are provided in Table 17. Subjects must be fasting (at least 8 hours) for Visit 1 (Screening) and, if possible, at Visit 8 (EOS). However, if a subject arrives at the clinic for Visit 8 (EOS) without fasting for at least 8 hours, laboratory specimens may be collected as non-fasting, at the discretion of the Investigator and documented as such on the laboratory requisition form.
- i. Assessments will be made after the subject has rested in a seated position for at least 5 minutes. Height and weight will also be measured at Visit 1 (Screening).

- j. The term WOCBP is defined in [Appendix 4](#).
- k. All urine pregnancy tests must have a minimum sensitivity of 25 mIU β -hCG/mL.

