Ages 18+ yrs	NA: 10.5mL	NA: 10.5mL	NA: 10.5mL	NA: 31.5mL	NA: 10.5mL
	EU: 14mL	EU: 14mL	EU: 14mL	EU: 42mL	EU: 14mL

Total Blood Volume Maximal Use Arm

	Screening V1	V2	V3	V4	V5	EOS/EOT V8	TOTAL	UNS
Ages 6-11 yrs	NA: 3.5mL	NA: 8mL	NA:0	NA:8mL	NA:0	NA 3.5mL	NA: 23mL	NA:3.5mL
	EU: 6mL	EU: 8mL	EU:0	EU: 8mL	EU:0	EU: 6mL	EU: 28mL	EU: 6mL
Ages 12-17 yrs	NA: 5.5mL	NA: 24mL	NA:4mL	NA: 24mL	NA:4mL	NA: 9.5mL	NA: 71mL	NA: 5.5mL
	EU: 8mL	EU: 24mL	EU: 4mL	EU: 24 mL	EU: 4mL	EU: 12mL	EU: 76mL	EU: 8mL
Ages 18+ yrs	NA: 10.5mL	NA: 24mL	NA:4mL	NA: 24mL	NA:4mL	NA: 14.5mL	NA: 81mL	NA:8mL
	EU: 14mL	EU: 24mL	EU: 4mL	EU: 24mL	EU: 4mL	EU: 18mL	EU: 88mL	EU: 14mL

Table 17 Protocol-Required Safety Laboratory Assessments

Category	Parameters
Hematology	
 Red blood cell counts (Indices: Mean Corpuscular Volume, Mean Corpuscular Hemoglobin, % Reticulocytes) Hemoglobin, Hematocrit, Platelets, White blood cell count (Neutrophils, Lymphocytes, Monocytes, Eosinophils, Basophils)
Clinical Chemistry	
 Sodium, Potassium, Calcium Corrected, Magnesium, Bicarbonate Aspartate Aminotransferase (AST)/Serum Glutamic-Oxaloacetic Transaminase (SGOT), Alanine Aminotransferase (ALT)/Serum Glutamic-Pyruvic Transaminase (SGPT), Alkaline Phosphatase Total and Direct Bilirubin, Total Protein Fasting lipid panel (Screening, Week 12 and Week 24)
Routine Urinalysis	
 Specific Gravity pH, Glucose, Protein, Blood, Ketones, (Bilirubin, Urobilinogen, Nitrite, Leukocyte Esterase) by Dipstick Microscopic Examination (if blood or protein is abnormal)
Other Screening Tests	
 Urine/Serum Human Chorionic Gonadotropin (hCG) Pregnancy Test (as indicated in the SoA Table 1 and Table 13 and for Women of Childbearing Potential) All study-required laboratory assessments will be performed by a central laboratory, with the exception of urine pregnancy testing.

Appendix 3: Adverse Events: Definitions and Procedures for Recording, Evaluating, Follow-up, Reporting

Definition of AE

AE Definition

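### Exclusion criterion 15 sets a creatinine limit, but the required central-laboratory panel (Protocol Table 17) does not include creatinine

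*Protocol*

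**What the plan says.** Criterion 15 appears in Protocol 5.2 and again in the Synopsis. It excludes subjects with ALT or AST above 2 times the "Upper Limit of Normal (ULN) and/or creatinine" above 1.5 times ULN. Unlike criterion 5, it has no exemption for the Optional Maximal Use arm, so it applies to both parts of the study.

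Protocol 8 makes the check mandatory: "All screening evaluations must be completed and reviewed to confirm that potential subjects meet all eligibility criteria". The same section rules out waivers.

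For the tests themselves, Protocol 8.3.4 refers to Appendix 2 "for the list of clinical laboratory tests to be performed". For the maximal-use arm, footnote h to Table 13 says: "Clinical laboratory tests (hematology, clinical chemistry, routine urinalysis) are provided in Table 17". The matching footnote j to Table 1, for the main study, has a broken cross-reference and supplies no other panel.

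The Clinical Chemistry row of Table 17 includes "Alanine Aminotransferase (ALT)/Serum Glutamic-Pyruvic Transaminase (SGPT), Alkaline Phosphatase" (AST is on the same line) and "Total and Direct Bilirubin, Total Protein". The table also states that "All study-required laboratory assessments will be performed by a central laboratory", with urine pregnancy testing as the only exception. Appendix 2 refers back to Section 5 for entry requirements and lets the investigator, or local regulations, call for additional tests.

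**The concern.** A numeric laboratory exclusion needs a laboratory test to apply it. A site that runs the required panel exactly as written learns whether a subject passes the hepatic limits and learns nothing about the creatinine limit. It must then decide for itself how to meet the obligation in Protocol 8. Sites could reasonably differ: one might order a local creatinine, another might rely on history.

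The renal limit has a stated rationale. Protocol 2.3 lists, among the notable adverse reactions of oral isotretinoin, "renal or hepatotoxicity, musculoskeletal discomfort, and visual acuity reduced". Criterion 15 pairs a hepatic with a renal limit, and the panel supports only the hepatic one. What is at stake is uniform application of a safety exclusion and a documented record that it was applied.

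**Working it through.** No calculation applies. The check sets each analyte in criterion 15 against every row of Table 17, then looks for any other sentence that orders the missing test.

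**Step 1. Criterion against panel.**

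| Analyte in criterion 15 | Limit | Listed in Table 17? |
|---|---|---|
| ALT | above 2 × ULN | Yes, Clinical Chemistry |
| AST | above 2 × ULN | Yes, Clinical Chemistry |
| Creatinine | above 1.5 × ULN | No, in any row |

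By row, Table 17 contains:
- Hematology: blood counts and indices.
- Clinical Chemistry: sodium, potassium, magnesium, bicarbonate, corrected calcium, AST, ALT, alkaline phosphatase, bilirubin (total and direct), total protein and fasting lipids.
- Routine Urinalysis: dipstick measures, with microscopy if blood or protein is abnormal.
- Other Screening Tests: hCG only.

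The required panel therefore covers 2 of 3 analytes.

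**Step 2. Other mentions.** Creatinine occurs only in the two copies of criterion 15. SAP 7.3 (Clinical Laboratory Data) names no individual analytes.

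**Step 3. Sentences that might close the gap.**
- Protocol 8 obliges sites to confirm the criterion but orders no test.
- Appendix 2 points to Section 5 for entry requirements. Section 5 gives the limit but no test.
- Appendix 2 permits additional tests. That is permission and not a requirement.
- Appendix 1 (Data Quality Assurance) requires source data to support eCRF entries and monitors to verify them. This may reveal a missing creatinine afterwards but does not cause one to be measured.

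None of these adds creatinine to the required panel.

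**Step 4. Reach.** The criterion covers the roughly 110 planned main-study subjects and the roughly 32 in the maximal-use arm (110 + 32 = 142).

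**The case against.** The strongest reply is that this is a one-word slip in a list and that the surrounding procedures already cover it. Appendix 2 refers to Section 5, so creatinine could be read as study-required and hence as a central-laboratory test. Confirmation of eligibility is compulsory, waivers are barred, and monitoring against source should show up a criterion marked as met with no value behind it. Much of this stands: sites have no licence to skip the check, and the criterion can be applied. But reaching creatinine this way takes inference, while the table headed as the required assessments leaves it out.

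A second reply is that Table 17 may not be the full assay list. It includes corrected calcium without albumin, which that correction normally needs, and SAP 7.3 mentions serology results that Table 17 does not contain. A line could also have been lost in reading the PDF. These points limit confidence. Against them, the chemistry entries read as complete, with no redaction mark or visible gap, and an assay run outside the written protocol would still leave the protocol inconsistent.

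A third reply is that the risk is small. The toxicity statement concerns oral isotretinoin, Protocol 2.3 expects low systemic exposure from topical use, and inclusion 9 and exclusion 14 give general protection. This stands, and it sets the weight of the point.

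A reader might go further and infer that subjects with impaired renal function were probably enrolled, or try to estimate how many. The documents do not support this. They give no frequency of creatinine above 1.5 × ULN, and any such estimate would also have to assume that sites did not test, contrary to Protocol 8.

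**Conclusion.** The inconsistency is real and minor. Of the three analytes on which criterion 15 depends, the required panel measures two. The renal limit can be checked only through a discretionary test outside that panel, although confirmation of the criterion is mandatory. Clinical risk is low, and sample size, alpha, power and the efficacy analyses are unaffected. It still merits correction because the remedy is specific and inexpensive and serves subject safety.

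The conclusion rests on Table 17 being complete as it appears in the protocol. The laboratory's operational documents, which are not part of the protocol or SAP, could show that creatinine was measured in practice. That would settle the matter for enrolled subjects but would not mend the protocol text. The documents do not support the stronger claims that the criterion cannot be applied or that ineligible subjects entered.

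**What to change.** Add serum creatinine to the Clinical Chemistry row of Table 17, run by the central laboratory on the chemistry sample already taken at Screening, for both the main study and the maximal-use arm. It would then repeat with the panel at Week 12 and end of study in the main study, and at end of study in the maximal-use arm. That is a side benefit and not something criterion 15 requires. Before the change, the laboratory should confirm that the Screening volume for ages 6 to 11 (3.5 mL in North America, 6 mL in Europe, per Appendix 2) is enough for the extra analyte.

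For subjects already enrolled, check the by-subject laboratory listing planned in SAP 7.3 and the source records for a Screening creatinine, and state in the study report how criterion 15 was verified. The inclusion/exclusion listing in SAP 4.1 is not described as carrying laboratory values, so it cannot be relied on for this.

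The cost is one analyte on an existing sample, with no added visit, plus a small amendment that needs IRB/IEC approval and, where applicable, regulatory approval. The amendment helps only subjects screened after approval. SAP Version 3.0 is dated 27 February 2024, and its later addendum already reports on baseline scores. This suggests that enrolment was well advanced, though no closing date is given. If screening has ended, the retrospective check and its disclosure are the useful part.
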